Pilot Mobile for Dementia and Frailty (Mindful Meals)

NCT05827094

April 23, 2023

STUDY PROTOCOL

Objective

We conducted a pilot randomized controlled trial (RCT) to assess the feasibility and preliminary efficacy of an innovative, theory-driven mobile intervention specifically designed for older adults with frailty and dementia, aimed at increasing Mediterranean food consumption. Primary efficacy outcome was adherence to the Mediterranean diet score.

Design

This was a pilot randomized control trial (RCT) to test the feasibility and preliminary efficacy of a mobile intervention consisting of a patient-facing mobile app and a secure web-based administrative dashboard. Participants were randomly assigned to either the intervention group or the control group. Those randomized to the intervention received access to a mobile app, available for download by invitation only on the Apple App Store. Participants randomized to control received via email referral to National Institute on Aging (NIA) materials concerning healthy eating.

Methods

Participants

Eligibility criteria included: a) being age 65 years and older, b) having difficulty with at least one of the following activities: performing heavy housework; performing light housework; walking outside alone; managing money/paying bills; shopping for personal items; preparing meals, suggestive of frailty, 3) being diagnosed with early dementia or having memory symptoms suggestive of mild cognitive impairment. Exclusion criteria included: a) having difficulty with basic activities of daily living such as eating and getting

out of bed, suggestive of overt disability, b) having a 14-item Mediterranean Diet Adherence Screener (MEDAS) >8, suggestive of an optimal diet, d) severe hearing or visual impairment.

STATISTICAL ANALYSIS PLAN

Descriptive statistics were first calculated to compare demographic characteristics between the intervention and the control groups. Outcomes measures were analyzed by calculating the within-group pretest–post-test change scores and then comparing the change scores between the intervention and the control groups using Mann–Whitney U tests. To estimate the magnitude of the intervention's impact compared to the control group, we used Hedges' g to measure effect size. Hedges' g is a variation of Cohen's d that corrects for biases that may occur in small sample sizes, making it a more appropriate choice for our study. Hedges' g takes the difference in means between the intervention and control groups and divides it by the pooled standard deviation while applying a correction factor to account for potential biases. A larger absolute value of Hedges' g indicates a greater effect size, with values of 0.2, 0.5, and 0.8 generally considered small, medium, and large effect sizes, respectively. An R package, "BootES" was used to calculate 95% bootstrap confidence intervals for the effect sizes. The "BootES" package is designed specifically for this purpose, providing a robust and efficient method for estimating confidence intervals based on resampling techniques. Finally, descriptive statistics and visual analytics were used to describe app quality and to analyze log data of user interactions.

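### Does an app offered only through the Apple App Store, with no device criterion printed, call for a change to eligibility or analysis?

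*Combined protocol and SAP*

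**What the plan says.** The Design section describes the intervention as "a patient-facing mobile app and a secure web-based administrative dashboard". On how participants obtained the app it says: "Those randomized to the intervention received access to a mobile app, available for download by invitation only on the Apple App Store". The dashboard is administrative and is not presented as a way in for participants, so one route is named. The comparator needs no Apple device: "Participants randomized to control received via email referral to National Institute on Aging (NIA) materials concerning healthy eating". On allocation the section says only: "Participants were randomly assigned to either the intervention group or the control group". It describes no device check beforehand.

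Under Methods, Participants, the inclusion list begins "Eligibility criteria included: a) being age 65 years and older, b) having difficulty with at least one of the following activities" and ends with cognitive status. The exclusions are disability in basic activities, a MEDAS above 8, and severe hearing or visual impairment. Those six printed criteria include none on a device or an email address. The last inclusion item is labelled 3 after a and b, and the exclusions run a, b, d.

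The SAP takes each participant's change score, "then comparing the change scores between the intervention and the control groups" by Mann–Whitney test, with Hedges' g and a bootstrap interval for size. Separately, "descriptive statistics and visual analytics were used to describe app quality and to analyze log data of user interactions". It has no rule for people who could not install the app and no exclusion on that ground.

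**The concern.** The barrier would fall on one arm only. A person aged 65 or over without an Apple device can receive an emailed referral but cannot install an app from the Apple App Store. If such people were randomised to the app and not lent a device, two things could go wrong.

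First, the comparison of all participants as randomised would be diluted, and the SAP reads g against benchmarks of 0.2, 0.5 and 0.8. Second, feasibility is a stated objective. People who could not obtain the app and people who had it and ignored it both leave no interactions in a log, although the two point to different remedies.

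A third possibility is worse in kind: dropping people without a device from the app arm alone would break the balance that randomisation gives.

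**Working it through.** **Text check.** Criteria on a device among the six printed: 0. Statements of device loan or provision: 0. Routes to the app named: 1. The literal reading is therefore correct. It rests on silence, however, in lists that are not presented as complete and whose lettering skips an item. The gap at c may be a lost criterion or a mislabelled item; the inclusion list has a labelling slip of its own. The documents do not settle which.

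**Dilution.** The documents give no sample size, SD, effect or share unable to install, so every input here is an assumption:

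- q is the share of the app arm unable to install, shown from 0 to 30%.
- Those people change like controls.
- SD is 1 in each part, and the true standardised effect d is 0.5 or 0.8.

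The app arm is then a mixture of (1−q) with mean d and q with mean 0. Its variance is 1 + q(1−q)d². Pooling with a control variance of 1, for equal arms, gives

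g(q) = (1−q)d / √(1 + q(1−q)d²/2).

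For d = 0.5 and q = 0.1: 0.45 / √1.01125 = 0.45. For d = 0.5 and q = 0.3: 0.35 / √1.02625 = 0.35. For d = 0.8 and q = 0.1: 0.72 / √1.0288 = 0.71.

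The probability that a random app participant's change exceeds a random control's, which is the Mann–Whitney scale, is (1−q)Φ(d/√2) + 0.5q. For d = 0.5, Φ(0.354) = 0.638. At q = 0.1 this gives 0.9 × 0.638 + 0.05 = 0.624.

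| q | g if d = 0.5 | g if d = 0.8 | Mann–Whitney probability, d = 0.5 |
|---|---|---|---|
| 0% | 0.50 | 0.80 | 0.638 |
| 10% | 0.45 | 0.71 | 0.624 |
| 20% | 0.40 | 0.62 | 0.611 |
| 30% | 0.35 | 0.54 | 0.597 |

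**One-sided exclusion.** Let b be the difference in mean change between people with and without a device. If people without a device were removed from the app arm only, controls would still contain their share q. The expected difference becomes d + qb, so the bias is qb. With b assumed to be 0.2 SD it is 0.1 × 0.2 = 0.02, 0.2 × 0.2 = 0.04 and 0.3 × 0.2 = 0.06 SD at q = 10, 20 and 30%. With b = 0 it is zero. The SAP calls for no such exclusion.

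**Does the planned analysis cope?** Controls are not given the app, yet they need change scores for the comparison, so outcome measurement cannot depend on the app alone. A participant who could not install it could still supply a change score and be analysed in the assigned arm. The result then estimates the effect of offering the app, which is a legitimate target in a pilot.

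**The case for a change.** The strongest case for acting is that feasibility is half of the objective, and whether people can obtain the app is central to it. An invitation to download does not supply a device, so the statement that the app arm received access does not prove installation. Analysis as randomised guards against selection bias but does not say why the app went unused. The doubt about the lists cuts both ways, since a reader cannot tell whether device access was required. Settling the matter would cost one sentence and one count.

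Most of this stands as a remark on reporting. A reader would like to know whether devices were required or supplied, what became of exclusion item c, and how many in the app arm never installed. It does not show a fault in the plan. The received-access statement is the only one bearing on the question, and its ordinary sense is that the arm obtained the app. The SAP does not list the logged events, so it cannot be assumed that the log fails to separate never-opened from little-used, although a log alone would not explain why an app was never opened. Inability to install is also itself a feasibility finding, which the investigators would meet on issuing invitations and would naturally describe.

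**Conclusion.** No change to the plan follows. The documents name one route to the app and do not say how device access was assured. They do not show that anyone unable to install was enrolled, and no stated rule gives a wrong result. The dilution figures (a true g of 0.5 seen as 0.45 to 0.35 for q of 10 to 30%) hold only for an assumed q and for non-installers who change like controls. At q = 0 there is no loss. The bias of 0.02 to 0.06 SD needs both an assumed b and an exclusion that the SAP does not contain.

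A device requirement before randomisation cannot be added to a study already reported in the past tense, and analysis without device-related exclusions is what the SAP already implies. What is left is a gap that the investigators can fill sensibly when they describe recruitment and app uptake. This conclusion would change only if there were evidence that people without a device were randomised and then removed from one arm.

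### Do entry rules wider than the 'dementia and frailty' label, with only demographics named at baseline, call for a change to the plan?

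*Combined protocol and SAP*

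**What the plan says.** The study title is "Pilot Mobile for Dementia and Frailty", and the Objective calls the intervention "specifically designed for older adults with frailty and dementia". Under Methods, Participants, the cognitive criterion is met by "being diagnosed with early dementia or having memory symptoms suggestive of mild cognitive impairment", so a diagnosis is one of two routes and no minimum share is set for either. The functional criterion is "having difficulty with at least one of the following activities", followed by a list of six. Heavy housework alone would qualify, and the protocol says only that such difficulty suggests frailty.

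The SAP's baseline sentence reads "Descriptive statistics were first calculated to compare demographic characteristics between the intervention and the control groups". Outcomes are then analysed by "comparing the change scores between the intervention and the control groups" with Mann–Whitney U tests, together with Hedges' g and bootstrap 95% intervals. The other descriptive statistics cover app quality and log data. Nothing in the SAP mentions cognitive route or qualifying activity.

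**The concern.** Read side by side, the label joins two conditions with *and*, while the cognitive entry rule offers two routes joined by *or*. A participant with memory symptoms, no dementia diagnosis and trouble with heavy housework would be eligible. By the wording, anywhere from 0% to 100% of the sample could have diagnosed dementia, and no analysis named in the SAP would narrow that range.

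The stake is attribution. Feasibility is a stated aim, and the ability to use an app may well depend on cognitive status. Someone planning a full trial would want to know whether retention, app use and change in diet score came from people with diagnosed dementia, from people with symptoms only, or from both, and whether the arms differed in that mix.

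**Working it through.** The documents give no sample size, allocation ratio, target effect or mix, so there is no figure of the plan's own to reproduce. The check has a textual part and an illustrative part.

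**Text**

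| Place | What it describes | Who is covered |
|---|---|---|
| Study title | Short name | Dementia and frailty |
| Objective | The app's intended users | Frailty and dementia |
| Methods, Participants | The enrolled sample | Early dementia *or* memory symptoms, plus difficulty with at least one of six activities |
| SAP, baseline sentence | Arm comparison | Demographic characteristics |
| SAP, outcome sentences | Arm comparison | All participants, by arm |

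Only the Participants section defines the sample, and it hedges both conditions as suggestive. The SAP then compares the arms in that sample, so there is no conflict between the population enrolled and the population analysed.

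**Illustration 1: could the mix reverse the reading of the pooled effect?** Assume zero effect in diagnosed dementia, a share *p* diagnosed, a common SD and a pooled g of 0.5 (the SAP's medium benchmark). Then g in the symptoms-only group = 0.5 / (1 − p):

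- p = 0.10: 0.5/0.90 = 0.56
- p = 0.25: 0.5/0.75 = 0.67
- p = 0.50: 0.5/0.50 = 1.0
- p = 0.75: 0.5/0.25 = 2.0

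This identity holds for any unreported subgroup and says nothing particular about this trial. It also treats 0.5 as known. With n per arm, SE ≈ √(2/n + g²/(4n)), and the approximate 95% interval is 0.5 ± 1.96 × SE:

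- n = 10: SE = √(0.2 + 0.00625) = 0.454; interval -0.39 to 1.39
- n = 20: SE = √(0.1 + 0.003125) = 0.321; interval -0.13 to 1.13
- n = 30: SE = √(0.0667 + 0.0021) = 0.262; interval -0.01 to 1.01

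Each interval includes zero for the whole sample, though only just at n = 30, so knowing *p* would seldom change what such a pilot supports.

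**Illustration 2: chance imbalance in diagnosis.** Assume simple 1:1 randomization with the numbers diagnosed in the two arms independent Binomial(n, p).

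| p | n per arm | P(20 points or more apart) | P(more than 20 points apart) |
|---|---|---|---|
| 0.50 | 10 | 50% | 26% |
| 0.50 | 20 | 27% | 15% |
| 0.50 | 30 | 15% | 9% |
| 0.25 | 10 | 43% | 19% |
| 0.25 | 20 | 20% | 10% |
| 0.25 | 30 | 10% | 5% |

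About half of most entries comes from counting a gap of exactly 20 points. Imbalance also matters only if diagnosis predicts change in diet score. If it shifted change by 0.5 SD (assumed), a 20-point gap would move the contrast by 0.20 × 0.5 = 0.10 SD, against a standard error of about 0.32 SD at 20 per arm. The test and interval already allow for chance imbalance of this kind.

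**The case for a change.** The strongest case for acting is that the remedy costs almost nothing. Eligibility had to be assessed, so diagnosis status may well have been recorded. One extra baseline row would tell the planner of a full trial whether a pooled result says much or little about dementia. If the Objective describes only the app's intended users, that is a further reason to say how closely the sample matches them. The title carries the narrower label too. The case asks for no subgroup test and claims no bias in the randomized comparison.

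Most of this stands as advice on reporting: a count by cognitive route and arm is useful, and a report should describe the population as the entry rules do. It does not amount to a fault in the plan. The document is a short past-tense summary, and *demographic characteristics* in a one-paragraph SAP may be loose wording for the usual baseline table. The documents do not show whether screening kept the two routes apart, nor whether the results gave the counts. Analysing both routes together is the expected analysis for a pilot, and the suggested remedy would leave it untouched.

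**Conclusion.** The observation is accurate, but no change to the plan follows. The label is narrower than the entry rules, and the SAP does not name counts by cognitive route. Even so, the plan followed exactly as written gives a valid comparison for the population that the Participants section defines. What is missing is descriptive detail that analysts would ordinarily supply at the reporting stage, and supplying it would change no estimate, test or interval.

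The sizes above are illustrations that rest on assumed arm sizes of 10 to 30, assumed shares diagnosed, simple randomization and, in the first, zero effect in diagnosed dementia. On those assumptions, sampling error outweighs anything that the mix could settle: a pooled g of 0.5 has an interval that includes zero at each size, and a 20-point imbalance moves the contrast by about 0.10 SD against a standard error of about 0.32 SD at 20 per arm. A much larger sample or effect would make the mix more informative, but the comparison would still be valid.

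### The change-score comparison and Hedges' g are valid but not adjusted for the pretest; an added pretest-adjusted estimate would usually be somewhat more precise and would remove the share of chance imbalance that subtraction leaves in

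*Combined protocol and SAP*

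**What the plan says.** The Statistical Analysis Plan is one paragraph, written in the past tense. On outcomes it says: "Outcomes measures were analyzed by calculating the within-group pretest–post-test change scores", followed by "comparing the change scores between the intervention and the control groups using Mann–Whitney U tests". The size of the effect is given by Hedges' g, which "takes the difference in means between the intervention and control groups and divides it by the pooled standard deviation", with a small-sample correction. The plan does not say whether these are means of change or of post-test scores. The only interval is for g: a bootstrap package "was used to calculate 95% bootstrap confidence intervals for the effect sizes". The plan supplies its own reading scale for g: "values of 0.2, 0.5, and 0.8 generally considered small, medium, and large effect sizes, respectively".

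No regression, ANCOVA or other pretest-adjusted analysis appears. The one baseline comparison named is of demographics: "Descriptive statistics were first calculated to compare demographic characteristics between the intervention and the control groups". The plan does not say whether pretest outcome scores were also shown by arm.

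In the Study Protocol, the Objective states: "Primary efficacy outcome was adherence to the Mediterranean diet score". MEDAS appears only under Methods, Participants, as an exclusion: "having a 14-item Mediterranean Diet Adherence Screener (MEDAS) >8, suggestive of an optimal diet". That the outcome score is also MEDAS is therefore an inference.

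**The concern.** A change score uses the pretest, but with its coefficient fixed at 1. When pretest and post-test SDs are similar and the score is not perfectly repeatable, the true slope is below 1. Two things follow for the difference in mean change. It usually has a larger variance than the adjusted difference. And if the arms differ by chance at pretest by D points, (1 − slope) × D stays in the estimate, favouring the arm that started lower. If g is instead built on post-test means, the slope is fixed at 0: g is still unadjusted and keeps slope × D, favouring the arm that started higher.

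Preliminary efficacy is one of the pilot's two aims, and g is the figure that readers will set against the 0.2 / 0.5 / 0.8 scale. Arms in a pilot are likely to be small, so a chance pretest difference could account for part of that figure. The pretest is already in hand, because the change score needs it.

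**Working it through.** **Inputs.** The documents state no sample size, allocation ratio, SD, correlation or target effect, so there is no plan figure to reproduce and every number below is assumed. Base case: integer score, mean 7, SD 2 before and after, kept if the pretest is 8 or below (the cut-off is from Methods, Participants). Screening reduces the pretest SD to 1.49 (variance 2.22). Correlation before screening, rho, is 0.4 to 0.7. With equal SDs the slope equals rho. Arms are equal, n = 20 or 10 each; N = 2n. Planned g is taken to be on change.

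**1. Precision.** Per-person variance:
- change: V = (1 − rho)² × 2.22 + (1 − rho²) × 4
- adjusted: A = (1 − rho²) × 4

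Variance ratio, adjusted to change: (A / V) × (N − 3)/(N − 4). The last factor is the price of estimating the slope: 37/36 at 20 per arm, 17/16 at 10 per arm.

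| rho | A | V | ratio, n = 20 | ratio, n = 10 |
|---|---|---|---|---|
| 0.4 | 3.36 | 0.36 × 2.22 + 3.36 = 4.16 | 0.83 | 0.86 |
| 0.5 | 3.00 | 0.25 × 2.22 + 3.00 = 3.56 | 0.87 | 0.90 |
| 0.6 | 2.56 | 0.16 × 2.22 + 2.56 = 2.92 | 0.90 | 0.93 |
| 0.7 | 2.04 | 0.09 × 2.22 + 2.04 = 2.24 | 0.94 | 0.97 |

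The variance falls by 6 to 17% at 20 per arm and 3 to 14% at 10 per arm. In standard error at 20 per arm this is about 3 to 9% (√0.94 = 0.97, √0.83 = 0.91). Simulation of the rounded, screened score agrees to within about 0.01.

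**2. What a chance imbalance does to g.** With no true effect and the intervention arm 1 point lower, expected g is about (1 − rho)/√V × J. At 20 per arm, J = 1 − 3/(4 × 38 − 1) = 0.98.
- rho 0.4: 0.6/2.04 × 0.98 = 0.29
- rho 0.5: 0.5/1.89 × 0.98 = 0.26
- rho 0.6: 0.4/1.71 × 0.98 = 0.23
- rho 0.7: 0.3/1.50 × 0.98 = 0.20

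Simulated trials with the intervention arm 0.85 to 1.15 points lower averaged 0.28 / 0.25 / 0.22 / 0.19; adjusted g averaged close to 0. In those trials the Mann–Whitney test rejected in about 8 to 11%, against about 5% for ANCOVA. At a half-point imbalance, g averages 0.10 to 0.14 and the total Mann–Whitney error is nominal, though lopsided towards the intervention.

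**3. How often.** The standard error of the pretest difference is 1.49 × √(2/20) = 0.47 at 20 per arm and 1.49 × √(2/10) = 0.67 at 10 per arm. The intervention arm starts at least 1 point lower in about 2% and about 8% of simulated trials respectively, and at least half a point lower in about 16% at 20 per arm. The control arm does so equally often, which pulls g the other way.

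**4. Where the gain vanishes.**
- At rho 0.8 and 10 per arm: 1.44/(0.04 × 2.22 + 1.44) × 17/16 = 1.00, so no gain.
- With post-test SD 3, the slope is rho × 3/2. At rho 0.4 (slope 0.6) and 10 per arm: 7.56/(0.16 × 2.22 + 7.56) × 17/16 = 1.01. At rho 0.7 (slope 1.05) the ratio is about 1.06, so adjustment is slightly less precise.

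**5. Choice of SD for an adjusted g.** At rho 0.4, a 1.5-point effect is 1.5/2.04 × 0.98 = 0.72 on the change SD but 1.5/1.49 × 0.98 = 0.99 on the screened pretest SD. Changing the divisor would move g by almost 0.3 in every trial. On the change SD the scale holds, and the sampling SD of g falls from about 0.33 to 0.30 (20 per arm, 1.5-point effect).

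**The case against.** The strongest reply is that nothing here is wrong. Mann–Whitney on change is a valid randomised comparison: its simulated error with no effect was close to 5% overall. The mean-change difference is unbiased over randomisation. The trial is a pilot, the precision gain is modest, and a 1-point imbalance is uncommon. All of this stands, and it is why the point is an improvement and not a correction.

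Three stronger readings are tempting, and the documents do not support them.

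- **That the planned comparison is biased, or carries the whole pretest imbalance.** Only (1 − slope) of it is kept: 0.3 points per point of imbalance at slope 0.7. It averages to zero over randomisation.
- **That ANCOVA should replace the rank test because it has more power.** For a 1.5-point effect at 20 per arm, power for Mann–Whitney against ANCOVA is 58 v 69% (rho 0.4) to 83 v 87% (rho 0.7) with near-normal scores. Part of that gap is rank versus mean, since a t-test on change lies in between. With strongly skewed residuals it reverses: 88 v 83% to 99 v 92%. The plan gives no information on the shape of the scores. The rank test's robustness does not extend to g, however, because g is a difference in means.
- **That pretest scores were not compared by arm.** The plan names demographics only. It is silent on pretest scores and does not exclude showing them.

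The past tense also suggests that the analysis has been run. That limits how an adjusted result may be presented, not whether it is useful.

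**Conclusion.** The point holds as a cheap improvement, at the level of something to consider. The planned test and effect size are valid; what they leave unused is the pretest as a covariate. Under the assumed inputs this costs a modest amount of precision and leaves g open to part of any chance imbalance. That part is enough to reach the plan's own small-effect mark in the uncommon trial where the intervention arm starts about 1 point lower.

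The size rests wholly on assumptions: a MEDAS-like outcome, equal arms, similar SDs before and after, correlation 0.4 to 0.7, and g on change scores. With very small arms and a high correlation, or a larger post-test SD, the precision gain can be nil or slightly negative. The actual gain in this trial cannot be determined from the documents.

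**What to change.** Keep Mann–Whitney on change as the planned test. For each outcome, add:

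- An ANCOVA of the post-test score on randomised group plus that outcome's own pretest score, reporting the adjusted difference in points with a 95% CI.
- A Hedges' g from that adjusted difference, divided by the same pooled SD as the planned g (the pooled SD of change scores, if g is on change), with the small-sample correction. State which means and which SD are used. Holding the divisor fixed keeps the 0.2 / 0.5 / 0.8 reading unchanged.
- A bootstrap interval for the adjusted g that refits the model in each resample.
- Pretest mean and SD by arm, without a significance test.

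If results are already known, label the adjusted difference and adjusted g as supplementary and leave the planned results as they are.

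Cost: one regression and a short bootstrap script per outcome, one degree of freedom, a few sentences of text and no new data. The downside is a possible slight loss of precision for the adjusted estimate in very small arms with high correlation.

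### Effect size is planned only as Hedges' g on unadjusted changes; a pretest-adjusted difference in diet-score points with a 95% CI should be added

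*Combined protocol and SAP*

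**What the plan says.** Under Objective, the protocol gives the aim and the endpoint: "We conducted a pilot randomized controlled trial (RCT) to assess the feasibility and preliminary efficacy", and "Primary efficacy outcome was adherence to the Mediterranean diet score". The only scale named is in the exclusion criteria under Participants: "having a 14-item Mediterranean Diet Adherence Screener (MEDAS) >8, suggestive of an optimal diet". The documents do not say that the same instrument is the outcome.

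The Statistical Analysis Plan sets out three steps.

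- **Variable analysed:** "Outcomes measures were analyzed by calculating the within-group pretest–post-test change scores".
- **Test:** "then comparing the change scores between the intervention and the control groups using" Mann–Whitney U tests.
- **Magnitude:** Hedges' g, which "takes the difference in means between the intervention and control groups and divides it by the pooled standard deviation" with a small-sample correction. It is read against fixed benchmarks, "with values of 0.2, 0.5, and 0.8 generally considered small, medium, and large effect sizes, respectively". For precision, the bootES package "was used to calculate 95% bootstrap confidence intervals for the effect sizes".

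No regression model or pretest covariate is named, and no mean or median difference in score points is given with an interval. The other descriptive statistics cover demographics, app quality and log data.

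**The concern.** A trial of preliminary efficacy on a diet score should tell the reader how many points the app added over control, and how precisely that is known. Hedges' g has no units, so g and its interval alone cannot answer either question. If g is scaled by the SD of change, as the order of the SAP suggests, it depends on the pre–post correlation as well as on the gain. The benchmarks of 0.2, 0.5 and 0.8 therefore do not correspond to a fixed number of points.

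The pretest score is also used only by subtraction. Entering it as a covariate usually gives a tighter estimate and accounts for chance pretest imbalance, which is more likely to matter in a small trial. Both gaps concern how the primary efficacy result is expressed. Neither makes the planned comparison wrong.

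**Working it through.** **Nothing to reproduce.** The documents state no sample size, SD, pre–post correlation, baseline mean, target difference or power. The omission can be read directly from the text; its size can only be illustrated.

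**Assumed inputs.** Outcome = MEDAS (0–14, whole points); entry capped at 8, from the exclusion criterion; before screening, mean 6–8, SD 2 and correlation ρ from 0.4 to 0.8.

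**Step 1: SD of change.** Without the cap, SD of change = SD × √(2(1 − ρ)):

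- ρ = 0.4: 2 × √1.2 = 2.19
- ρ = 0.8: 2 × √0.4 = 1.26

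A large simulation (bivariate normal, rounded, pretest ≤ 8 kept) gives 1.285 to 2.121, close to the formula.

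**Step 2: what g means in points.** Points = g × SD of change. For g = 0.5:

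- 0.5 × 1.285 = 0.64
- 0.5 × 2.121 = 1.06

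To isolate the correlation, ignore the cap and take a 1-point gain, SD 2 and 15 per arm. The small-sample factor is J = 1 − 3/(4 × 28 − 1) = 0.973, and g = J × 1/(2√(2(1 − ρ))). This gives 0.41, 0.49 and 0.63 at ρ = 0.3, 0.5 and 0.7. The same gain falls on either side of the SAP's 0.5 benchmark.

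**Step 3: precision in large samples.** Variance ratio, ANCOVA to change score = SDpost² (1 − r²) / SDchange², with r the correlation among those enrolled.

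- Without the cap and with equal SDs this is (1 + ρ)/2, or 0.70 to 0.90 for ρ = 0.4 to 0.8.
- With the cap, r is 0.262–0.725 and the ratio is 0.767–0.953. The cap narrows the spread of pretest scores and leaves less for adjustment to remove.
- CI width ratio: √0.767 = 0.876 and √0.953 = 0.976, so 2–12% narrower.
- Equivalent sample size: 1/0.953 = 1.05 and 1/0.767 = 1.30, so worth 5–30% more participants.

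**Step 4: precision in small samples.** Simulated trials (3,000 per setting; mean 6 and 8; ρ 0.4, 0.6, 0.8; true difference 1 point) give these mean 95% half-widths in points:

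| Per arm | Change score | ANCOVA |
|---|---|---|
| 10 | 1.19–1.97 | 1.20–1.78 |
| 20 | 0.82–1.35 | 0.81–1.20 |
| 30 | 0.66–1.09 | 0.65–0.97 |

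At 10 per arm with ρ = 0.8 there is no gain (width ratio 0.99–1.01). The t-based ANCOVA interval covered the true difference in 93.9–95.7% of trials.

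**Step 5: agreement with the planned test.** At a true difference of 1 point and 10–30 per arm, Mann–Whitney significance at 0.05 and an ANCOVA interval excluding zero disagreed in about 7–20% of simulated trials. For a t-interval on the unadjusted difference in mean change, the figure was about 4–7%.

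**The case against.** The strongest reply is that two matters are joined here, and only one needs a new model. An estimate in points does not require ANCOVA. The difference in mean change with its 95% CI would supply it, and that difference is already the numerator of g if g is on change scores. It also sits closer to the planned test (step 5). This stands as far as it goes, and the unadjusted difference can usefully be shown as well. But the plan commits to neither version, and pretest adjustment is a recognised improvement rather than a matter of taste.

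It can also be said that one trial has one SD of change, so a reader given that SD could convert g and, roughly, its interval. That is true, but the plan does not commit to reporting that SD. That g uses change scores is itself inferred from the preceding sentences. If post-test means were used instead, there would still be no interval in points and no pretest covariate.

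It is fair, too, that every input above is assumed, that this is a pilot, and that a rank test, a corrected effect size and an interval are already in place. These limit the weight of the point.

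Three stronger readings are tempting, and the documents support none of them.

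- **The planned analysis is biased or invalid.** The groups are randomised, so the comparison of changes is unbiased in expectation, and the Mann–Whitney p-value is unaffected.
- **A later trial could not be planned from these results.** A trial sized on the standardised change-score effect can use g. A difference in points would help, but is not strictly required.
- **A medium g could mean more points than a large one.** Across the assumed settings the two ranges just touch, but only by changing pretest mean and correlation together. With the mean held fixed, this holds barely at mean 6 and fails at 7 and 8.

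**Conclusion.** The point holds as a gap in how the effect is estimated and reported, not as an error of validity. No between-group difference in diet-score points with a 95% CI is planned, and the pretest score is not a covariate. That conclusion needs no assumption.

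Its size does rest on assumptions, because N, SD, correlation and baseline mean are not given and MEDAS is named only as a screener. Under the inputs listed, one value of g covers a range of points whose upper end is about 1.65 times its lower end (1.06/0.64). The precision gain from adjustment is modest and can vanish in a very small trial. The main benefit is an estimate that can be read in points. The change should be made, but nothing already planned has to be withdrawn.

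**What to change.** For the primary diet score, and any other outcome measured before and after, add the between-group difference in post-test points adjusted for the pretest score (ANCOVA), with its 95% CI. Keep the planned Mann–Whitney test and Hedges' g beside it.

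- The usual t-based interval is adequate. If a bootstrap is preferred, avoid a simple percentile interval at about 10 per arm, where simulated coverage was 90.7–92.6%.
- The unadjusted difference in mean change with its 95% CI may be shown too.
- The documents are written in the past tense. If outcomes have already been seen, keep the stated analysis as it is and label the new line as an added analysis.
- State which SD g uses; the context points to the SD of change.

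**Cost.** One extra line per outcome, from the pretest and post-test data that the change scores already require. The ANCOVA interval and the Mann–Whitney p-value may disagree, so the role of each should be stated. ANCOVA also assumes a common linear slope of post-test on pretest in the two arms.
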